### Appendix Table 2: Imaging and Treatment After First Radiologic Evidence of Progressive Disease

	Clinically Stable		Clinically Unstable	
	Imaging	Treatment	Imaging	Treatment
First radiologic evidence of PD by modified RECIST 1.1	Repeat imaging at 4 to 8 weeks to confirm PD.	May continue study treatment	Repeat imaging at 4 to 8 weeks to confirm PD per investigator's discretion only.	Discontinue treatment.
Repeat tumor imaging confirms PD (iCPD) by iRECIST per investigator assessment	No additional imaging required.	Discontinue treatment.	No additional imaging required.	Not applicable
Repeat tumor imaging shows iUPD by iRECIST per investigator assessment	Repeat imaging at 4 to 8 weeks to confirm PD. May occur at next regularly scheduled imaging visit.	Continue study treatment at the investigator's discretion.	Repeat imaging at 4 to 8 weeks to confirm PD per Investigator's discretion only.	Discontinue treatment.
Repeat tumor imaging shows iSD, iPR, or iCR by iRECIST per investigator assessment.	Continue regularly scheduled imaging assessments.	Continue study treatment at the investigator's discretion.	Continue regularly scheduled imaging assessments.	May restart study treatment if condition has improved and/or clinically stable per investigator's discretion. Next tumor imaging should occur according to the regular imaging schedule.

iCPD = confirmed progressive disease per iRECIST, iCR = complete response per iRECIST, iRECIST = modified Response Evaluation Criteria in Solid Tumors 1.1 for immune-based therapeutics, iSD = stable disease per iRECIST, iUPD = unconfirmed progressive disease per iRECIST, PD = progressive disease, RECIST 1.1 = Response Evaluation Criteria in Solid Tumors 1.1.

Eisai Confidential Page 123 of 138

### Appendix 3 Description of the Lugano and LYRIC Assessment of Response in Lymphoma

The Lugano criteria is based on a combination of metabolic and radiographic responses to characterize several components of lymphoma involvement including: nodal disease, extranodal disease, bone marrow disease, spleen and liver involvement, and clinical assessment. The standard assessment for tumor burden is CT for non-FDG avid lymphoma, and PET-CT for FDG-avid lymphoma. Standard definitions associated with the Lugano assessment are summarized in Appendix Table 3.

Responses should be determined on the basis of radiographic and clinical evidence of disease. Assessment of PET-CT should follow the recommendations for initial evaluation, staging, and response assessment for Hodgkin and non-Hodgkin's lymphoma; the Lugano classification described by Cheson (2014) is presented in the Revised Criteria for Response in Appendix Table 4.

In the context of immunotherapy, once PD is indicated by the Lugano criteria, the time point must then be confirmed as a true progression rather than an immune response by the LYRIC described by Cheson (2016). If the LYmphoma Response to Immunomodulatory Therapy Criteria (LYRIC) response does not qualify as true progression, it is called an Indeterminate Response (IR), which requires follow-up imaging as presented in Appendix Table 5.

#### Appendix Table 3: Standard Definitions and Assessments Lugano Lexicon

1. Baseline A	1. Baseline Assessments			
Lugano Measurement Terminology	Radiographic Measurement: Measureable lesions are characterized by the following radiographic parameters to describe lesion size by CT or MRI:  • LDi: longest transverse diameter of a lesion  • SDi: shortest axis perpendicular to the LDi  • PPD: cross product of the LDi and perpendicular diameter  • SPD: sum of the product of the perpendicular diameters for multiple lesions  FDG-PET Measurement: Measureable FDG-avid lesions are characterized by the FDG-PET 5-point scale (5-PS) (recommended by visual inspection of SUV images):  • Score 1: No uptake above background  • Score 2: Uptake ≤ mediastinum  • Score 3: Uptake > mediastinum, but ≤ liver  • Score 4: Uptake moderately > liver at any site			
	Score 5: Uptake markedly higher than liver at any site and/or new lesions			
Measurable (Target) Lesions	Measurable lesions must be accurately measured in at least one dimension with a minimum size of:			
	• >10 mm in the longest diameter (LDi) by CT or MRI scan (or no less than double the slice thickness) for non-nodal lesions and >15 mm in LDi for nodal			

Eisai Confidential Page 124 of 138

1

 
lesions
 
Identify up to 6 lesions including nodal masses or other lymphomatous disease
 

including extranodal disease measureable in 2 diameters (LDi and SDi)
Likely to be reproducible across all time points  Output  Description of the series and the series are series as a series and the series are series as a series are series are series are series are series as a series are series as a series are series ar
Representative of tumor burden  2. No decorated and containing a fitter to the decorated and all and a second about the containing a fitter to the cont

 
Nodes should preferably be from disparate regions of the body and should include, where applicable, mediastinal and retroperitoneal areas.
 

b. Non-nodal lesions include those in solid organs (eg, liver, spleen, kidneys, and lungs), gastrointestinal (GI) involvement, cutaneous lesions, or those noted on palpation.

 
For FDG-avid lesions, the target lesion should correlate with a co-registered FDG-PET lesion.
 

 
Product of perpendicular diameters (PPD) is used to characterize the size each lesion, PPD = LDi × SDi
 

Sum of product diameters (SPD) of all target lesions including nodal and non-nodal are reported as baseline SPD which is used for assessing tumor response at follow-up time points.
Bone marrow biopsy no longer indicated for the routine staging of HL and most DLBC. FDG-PET imaging should be used instead. Involvement determined by FDG avid disease in marrow.

 
For other lymphoma subtypes 2.5 cm unilateral bone marrow biopsy is recommended, along with immunohistochemistry and flow cytometry at screening/baseline
 

 
Splenomegaly is characterized by a >13 cm vertical length, as measured from cranial to caudal aspects by CT.
 

Nontarget lesions will include:
• Measurable lesions not selected as target lesions. Up to 10 nontarget lesions can be recorded at baseline.
All other disease not selected as target lesions consistent with lymphoma
Abnormal nodes, extranodal sites, assessable sites*
(*Cutaneous, gastrointestinal, bone lesions, pleural or pericardial effusions, ascites)

 
For FDG-avid lesions, the nontarget lesion should correlate with a co-registered FDG-PET lesion.
 

Nontarget lesions should be reported as present at baseline
Sum of product diameters at baseline = sum of the perpendicular product diameters, PPD = LDi $\times$ SDi, of each nodal and nonnodal target lesion. SPD = $\Sigma_n$ (PPD n ) where the subscript n denotes each target lesion.
Comprehensive history including

 
Absence/presence of fevers to >101 °F (38.3 °C)
 
Chills, drenching night sweats, or unexplained weight loss >10% of body mass over 6 months, and history of malignancy.
 
Fatigue, pruritus, and alcohol-induced pain in patients with HL should also be
 

noted.*  (*These factors rarely direct treatment, their recurrence may herald disease

Eisai Confidential Page 125 of 138

relapse.)					
2. Time Point	2. Time Point Assessments After Baseline				
Target Lesion Measurements	Radiographic measurement: Locate image that optimizes the LDi of the nodal and non-nodal target lesions. There is no need to go to an identical slice from baseline. Measure the respective LDi and SDi for all target lesions and calculate time point sum of product diameters (SPD timepoint ).				
	Special consideration for target lesions:				
	
 
If target lesion is too small to measure, a default value of 5 mm LDi and 5mm SDi should be entered on the eCRF.
 
				
	When no longer visible, enter 0 x 0 mm.				
	• For a node >5 mm × 5 mm, but smaller than normal, use actual measurement for calculation.				
	• If target lesion is between 5 to 10 mm, actual diameter should be entered on the eCRF.				
	• If target lesion splits into 2 or more lesion then the LDi and SDi and PPD of the split lesions will be added to the SPD and entered in place of that lesion.				
	• If 2 target lesion merged to form one lesion than the LDi and SDi of one should be entered as "0 x 0 mm" while the other lesion should have the LDi and SDi and PPD of the merged lesion				
	FDG-PET metabolic measurement: Locate each target lesion that is co-registered with CT imaging (maximum of 6) and use 5 point scale with an additional parameters to describe nonlymphoma-related FDG-uptake and nonevaluable lesions:				
	Score 1: No uptake above background				
	• Score 2: Uptake ≤ mediastinum				
	• Score 3: Uptake > mediastinum, but ≤ liver				
	• Score 4: Uptake moderately > liver at any site				
	• Score 5: Uptake markedly higher than liver at any site and/or new lesions				
	X : Area of new uptake unlikely to be related to lymphoma				
	NE : Not evaluable				
Nontarget Lesion Assessment	Nontarget lesions are evaluated by radiographic assessment qualitatively as present, regressed, absent, not evaluable (NE), or unequivocal progression.				
Definition of New Lesion	Any lesion which was not recorded at baseline. There is no minimum size criteria to identify a new lesion and clinical judgment must be used by the investigator.				
	May include a lesion in an anatomical location that was not scanned at baseline (ie, brain)				
	Should be unequivocal and not due to differences in scanning technique "x"				

5-PS = 5-point scale, CT = computed tomography, DLBC = diffuse large B-cell lymphoma, eCRF = electronic case report form, FDG-PET =  $^{18}$ fluorodeoxyglucose-positron emission tomography, HL= Hodgkin's lymphoma, MRI = magnetic resonance imaging, SUV = standardized uptake value.

Eisai Confidential Page 126 of 138

### **Appendix Table 4: Lugano Criteria for Response**

Response			CT-Based Response
Complete		Complete metabolic response	Complete radiologic response (all of the following)
	Lymph nodes and extralymphatic sites	Score 1, 2, or 3 a with or without a residual mass on the 5-PS b It is recognized that in Waldeyer's ring or extranodal sites with high physiologic uptake or with activation within spleen or marrow (eg, with chemotherapy or myeloid colony-stimulating factors), uptake may be greater than normal mediastinum and/or liver. In this circumstance, complete metabolic response may be inferred if uptake at sites of initial involvement is no greater than surrounding normal tissue even if the tissue has high physiologic uptake.	Target nodes/nodal masses must regress to ≤1.5 cm in LDi. No extralymphatic sites of disease.
	Nonmeasured lesion	Not applicable	Absent
	Organ enlargement	Not applicable	Regress to normal
	New lesions	None	None
	Bone marrow	No evidence of FDG-avid disease in marrow.  If the bone marrow was involved by lymphoma prior to treatment, the infiltrate must have cleared on repeat bone marrow biopsy.	If the bone marrow was involved by lymphoma prior to treatment, the infiltrate must have cleared on repeat bone marrow biopsy.
Partial		Partial metabolic response	Partial remission (all of the following)
	Nonmeasured lesion	Not applicable	Absent/normal, regressed, but no increase.
	Organ enlargement	Not applicable	Spleen must have regressed by >50% in length beyond normal (>13cm).
	New lesions	None	None
	Bone marrow	Residual uptake higher than uptake in normal marrow but reduced compared with baseline (diffuse uptake compatible with reactive changes from chemotherapy allowed). If there are persistent focal changes in the marrow in the context of a nodal response, consideration should be given to further evaluation with MRI or biopsy or an intervalscan.	Not applicable
No Response or		No metabolic response	Stable disease
Stable Disease	Lymph nodes and extralymphatic sites	Score 4 or 5 b with no significant change in FDG uptake from baseline at interim or end of treatment.	<50% decrease from baseline in SPD for up to 6 dominant, measurable nodes and extranodal sites; no criteria for progressive disease are met.
	Nonmeasured lesion	Not applicable	No increase consistent with progression.
	Organ enlargement	Not applicable	No increase consistent with progression.

Eisai Confidential Page 127 of 138

### Appendix Table 4: Lugano Criteria for Response

Response	Site	PET-CT-Based Response	CT-Based Response
	New lesions	None	None
	Bone marrow	No change from baseline	Not applicable
Progressive Disease		Progressive metabolic disease	Progressive disease (requires at least 1 of the following)
	Individual target nodes/nodal lesions	Score 4 or 5 b with an increase in intensity of uptake from baseline	An individual node/lesion must be abnormal with:  • LDi >1.5 cm AND  • Increase by ≥50% from PPD nadir AND  • An increase in LDi or SDi from nadir  • 0.5 cm for lesions ≤2 cm  • 1.0 cm for lesions >2 cm
	Extranodal lesions	and/or  New FDG-avid foci consistent with lymphoma at interim or end- of-treatment assessment.	An individual node/lesion must be abnormal with:  • LDi >1.5 cm AND  • Increase by ≥50% from PPD nadir AND  • An increase in LDi or SDi from nadir  • 0.5 cm for lesions ≤2 cm  • 1.0 cm for lesions >2 cm
	Nonmeasured lesion		New or clear progression of preexisting
	Organ enlargement		In the setting of splenomegaly, the splenic length must increase by > 50% of the extent of its prior increase beyond baseline (eg, 15 cm spleen must increase to >16 cm). If no prior splenomegaly, must increase by at least 2 cm from baseline.  New or recurrent splenomegaly.
	New lesions	and/or  New FDG-avid foci consistent with lymphoma rather than another etiology (eg, infection, inflammation). If uncertain regarding etiology of new lesions, biopsy or interval scan may be considered.	Regrowth of previously resolved lesions.  A new node > 1.5 cm in any axis.  A new extranodal site >1.0 cm in any axis; if <1.0 cm in any axis, its presence must be unequivocal and must be attributable to lymphoma.

Eisai Confidential Page 128 of 138

#### Appendix Table 4: Lugano Criteria for Response

Response	Site	PET-CT-Based Response	CT-Based Response
			Assessable disease of any size unequivocally attributable to lymphoma.
	Bone marrow	and/or  New or recurrent FDG-avid foci.	New or recurrent involvement

PS = 5-point scale, CR = complete response, CT = computed tomography, FDG = fluorodeoxyglucose, GI = gastrointestinal, LDi = longest transverse diameter of a lesion, MRI = magnetic resonance imaging, PET = positron emission tomography, PPD = cross product of the LDi and perpendicular diameter, PR = partial response, SDi = shortest axis perpendicular to the LDi, SPD = sum of the product of the perpendicular diameters for multiple lesions.

- a A score of 3 in many patients indicates a good prognosis with standard treatment, especially if scored at the time of an interim scan. However, in studies involving PET where de-escalation is investigated, it may be preferable to consider a score of 3 as inadequate response (to avoid under treatment).
- b PET 5-PS: 1, no uptake above background; 2, uptake \le mediastinum; 3, uptake \rightarrow mediastinum but \le liver; 4, uptake moderately \rightarrow liver; 5, uptake markedly higher than liver and/or new lesions; X, new areas of uptake unlikely to be related to lymphoma.

Source: Cheson, et al., 2014.

Eisai Confidential Page 129 of 138

#### Appendix Table 5: LYRIC PD Confirmation for Immunotherapy in Lymphomaa

LYRIC Measurement	Indeterminate Response (IR): This modification retains the core concepts of immunotherapy response criteria, incorporating			
Terminology	them into lymphoma-specific response criteria. Responses that are potentially due to immune reactions and characterized as			
	IR (as described below) require additional follow-up scanning to confirm disease progression.			
LYRIC PD and IR definitions	PD is the same as Lugano with the following exceptions that will qualify as IR:			
	• IR(1): ≥50% increase in SPD in first 12 weeks.			
	• IR(2): <50% increase in SPD with			
	a. New lesions(s), or			
	b. ≥50% increase in PPD of a lesion or set of lesions (including non-TL) at any time during treatment.			
	• IR(3): Increase in FDG uptake without a concomitant increase in lesion size meeting criteria for PD.			
LYRIC follow-up after IR for	In patients categorized as having any of the above types of IR, it is mandatory to obtain a repeat imaging after an additional			
PD confirmation	12 weeks (or earlier if clinically indicated). At that time, response should be re-evaluated, and the patient should be considered			
	to have true PD if the SPD of target lesion has increased further, with the considerations below:			
	• In the case of IR (1), the comparison should be between the first IR and the current overall tumor burden, with an			
	increase of $\geq$ 10% constituting PD. In addition there should be an increase of $\geq$ 5 mm for at least 1 lesions $\leq$ 2 cm, and			
	10 mm for lesions >2 cm (consistent with Lugano).			
	• In the case of IR(2), the new or growing (including non-TL) lesion(s) (unless biopsy proven benign) should be added to			
	the target lesion(s) up to a total of no more than 6 lesions. If the SPD of the newly defined set of target lesions has			
	increased ≥50% from their nadir value (which may precede IR) this patient would be considered PD.			
	• In the case of IR(3): Since inflammatory response may result in an increase in the standardized uptake value of a lesion,			
	the patient will not be considered to have progressive disease unless there is evidence of progressive disease by an			
	increase in lesion size or the development of a new lesions.			
Note on LYRIC PD time	If a patient is evaluated as IR and then "true" PD at a subsequent time point (without an intervening objective response			
point assignment	between IR and PD), the IR assessment should subsequently be corrected to PD for reporting purposes to the date of the prior			
	designation of IR. We recognize that these lesions may remain stable during the time of observation, but, even if this is the			
	case, the initial designation of IR should be changed to PD.			

a FDG = fluorodeoxyglucose, IR = Indeterminate Response, LYRIC = LYmphoma Response to Immunomodulatory Therapy Criteria, PD = progressive disease, PPD = product of perpendicular diameters, SPD = sum of product diameters, TL = target lesion.

Source: Cheson, et al. 2016.

Eisai Confidential Page 130 of 138

#### **Appendix 4** Cockcroft-Gault Calculation of Creatinine Clearance

Subjects must have adequate renal function as evidenced by serum creatinine  $\leq 1.8$  mg/dL or calculated creatinine clearance  $\geq 50$  mL/min per the Cockcroft–Gault formula as defined below.

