#### Measurable lesions are:

- a. Solid tumors: At least 1 lesion of ≥1 cm by longest axial diameter or ≥1.5 cm short axis diameter if a nodal lesion, which is serially measurable according to modified RECIST 1.1 using CT/MRI or photography. Lesions that have had external beam radiotherapy or locoregional therapies such as radiofrequency (RF) ablation must show evidence of progression to be deemed a target lesion (Appendix 2).
- b. Lymphoma: At least 1 lymph node with a longest diameter >1.5 cm or an extranodal lesion with a longest diameter >1.0 cm (Appendix 3).
- 6. Prior anticancer therapy such as chemotherapy, immunotherapy (eg, tumor vaccine, cytokine, checkpoint inhibitors), or investigational drugs, or any vaccine must have been completed at least 4 weeks before study drug administration, and all AEs must have either returned to baseline or stabilized. Subjects with prior immunotherapy known to have experienced severe nontolerable toxicities attributed to drug should be excluded.
- 7. Prior definitive radiation therapy must have been completed at least 6 weeks and prior palliative radiotherapy at least 2 weeks before study drug administration. Radiopharmaceuticals (eg, strontium, samarium) must be at least 8 weeks before study drug administration.
- 8. Immunosuppressive doses of systemic medications, such as steroids or absorbed topical steroids (doses >10 mg/day prednisone or equivalent) must have been discontinued at least 4 weeks before study drug administration.

Eisai Confidential Page 12 of 138

- 9. Subjects with prior Hepatitis B or C are eligible if they have adequate liver function as defined by Inclusion Criterion #13.
- 10. Left ventricular ejection fraction (LVEF) >50% or within normal limits per institutional practice, on echocardiography or multigated acquisition (MUGA) scan.
- 11. Adequate renal function defined as serum creatinine <1.5× ULN (or use SI units or calculated creatinine clearance ≥50 mL/min per the Cockcroft and Gault formula) (Appendix 4).
- 12. Adequate bone marrow function:
  - a. Absolute neutrophil count (ANC)  $\geq 1000/\text{mm}^3$  ( $\geq 1.0 \times 10^3/\mu\text{L}$ )
  - b. Platelets  $\ge 75,000/\text{mm}^3 (\ge 75 \times 10^9/\text{L})$
  - c. Hemoglobin ≥9.0 g/dL
- 13. Adequate liver function defined by:
  - a. Adequate blood coagulation function as evidenced by an International Normalized Ratio  $(INR) \le 1.5$

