## Translational approach

# 9.3 Selection of Study Population

Approximately 35 to 40 subjects will be enrolled in the Dose Escalation part and 80 subjects will be enrolled in the Dose Expansion part. Subjects who do not meet all of the inclusion criteria or who meet any of the exclusion criteria will not be eligible to receive study drug.

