#### 9.3.1 Inclusion Criteria

Subjects must meet all of the following criteria to be included in this study:

- 1. Age  $\geq$  18 years.
- 2. Eastern Cooperative Oncology Group (ECOG) Performance Status of 0 or 1.

Eisai Confidential Page 60 of 138

- 3. Life expectancy  $\geq 12$  weeks.
- 4. Subjects with solid tumors or lymphomas, confirmed by available histopathology records or current biopsy, that are advanced, nonresectable, or recurrent and progressing since last antitumor therapy, and for which no alternative standard therapy exists.
- 5. Subjects must have a minimum of one injectable lesion which is also accessible for biopsy, and if available, one other measurable lesion also accessible for biopsy. An injectable lesion is defined as being measureable (defined below) with a maximum of 3.0 cm longest diameter, accessible for injection as judged by the investigator, and has not been subjected to any prior intratumoral treatment or radiotherapy. Lesions selected for injection must not be too close to a major vessel, as judged by the investigator, and not be associated with increased risk of bleeding, eg, subcapsular liver lesions or hypervascular tumors.

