#### Measurable lesions are:

- a. Solid tumors: At least 1 lesion of ≥1 cm by longest axial diameter or ≥1.5 cm short axis diameter if a nodal lesion, which is serially measurable according to modified RECIST 1.1 using CT/MRI or photography. Lesions that have had external beam radiotherapy or locoregional therapies such as radiofrequency ablation must show evidence of progression to be deemed a target lesion (Appendix 1, Appendix 2).
- b. Lymphoma: At least 1 lymph node with a longest diameter >1.5 cm or an extranodal lesion with a longest diameter >1.0 cm (Appendix 3).
- 6. Prior anticancer therapy such as chemotherapy, immunotherapy (eg, tumor vaccine, cytokine, checkpoint inhibitors), or investigational drugs, or any vaccine must have been completed at least 4 weeks before study drug administration, and all AEs must have either returned to baseline or stabilized. Subjects with prior immunotherapy known to have experienced severe nontolerable toxicities attributed to drug should be excluded.
- 7. Prior definitive radiation therapy must have been completed at least 6 weeks and prior palliative radiotherapy at least 2 weeks before study drug administration.

  Radiopharmaceuticals (eg, strontium, samarium) must be at least 8 weeks before study drug administration.
- 8. Immunosuppressive doses of systemic medications, such as steroids or absorbed topical steroids (doses >10 mg/day prednisone or equivalent) must have been discontinued at least 4 weeks before study drug administration.
- 9. Subjects with prior Hepatitis B or C are eligible if they have adequate liver function as defined by Inclusion Criterion #13.
- 10. Left ventricular ejection fraction (LVEF) >50% or within normal limits per institutional practice, on echocardiography or multigated acquisition (MUGA) scan.
- 11. Adequate renal function defined as serum creatinine <1.5 × ULN (or use SI units or calculated creatinine clearance ≥50 mL/min per the Cockcroft and Gault formula [Appendix 4]).

Eisai Confidential Page 61 of 138

- 12. Adequate bone marrow function:
  - a. Absolute neutrophil count (ANC)  $\geq 1000/\text{mm}^3$  ( $\geq 1.0 \times 10^3/\mu\text{L}$ )
  - b. Platelets  $\ge 75,000/\text{mm}^3 (\ge 75 \times 10^9/\text{L})$
  - c. Hemoglobin ≥9.0 g/dL
- 13. Adequate liver function defined by:
  - a. Adequate blood coagulation function as evidenced by an International Normalized Ratio (INR)  $\leq$  1.5

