## 9.4.3 Method of Assigning Subjects to Treatment Groups

This is an open-label, single-arm study. All subjects who provide signed informed consent to participate in this study and satisfy all eligibility requirements (see Section 9.3) will be assigned to receive E7766. There is no randomization in this study.

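### Protocol Appendix 4 gives a creatinine limit (≤1.8 mg/dL) that differs from the one in Inclusion Criterion 11 (<1.5×ULN), which cites it

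*Protocol*

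**What the plan says.** The renal criterion appears in three places in the current protocol.

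- **Section 9.3.1, Inclusion 11:** "Adequate renal function defined as serum creatinine <1.5 × ULN", with a calculated clearance of at least 50 mL/min as an alternative. The reference to Appendix 4 sits inside the bracket, next to the formula.
- **Synopsis, Inclusion 11:** the same rule, "Adequate renal function defined as serum creatinine <1.5× ULN", with the alternative written as "calculated creatinine clearance ≥50 mL/min per the Cockcroft and Gault formula) (Appendix 4". Here the reference comes after the bracket that holds the alternative has closed.
- **Appendix 4**, before the Cockcroft-Gault formula: "Subjects must have adequate renal function as evidenced by serum creatinine $\leq 1.8$ mg/dL or calculated creatinine clearance $\geq 50$ mL/min".

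Three other statements bear on which text governs. Section 9.3 says "Subjects who do not meet all of the inclusion criteria or who meet any of the exclusion criteria will not be eligible". Section 9.3.1 opens with "Subjects must meet all of the following criteria to be included in this study". Section 9.4.3 assigns treatment to consenting subjects who "satisfy all eligibility requirements (see Section 9.3) will be assigned to receive E7766".

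**The concern.** Two current passages set different creatinine limits for one entry criterion, and the criterion itself points to the passage that differs from it. One limit scales with the local ULN and the other is fixed in mg/dL. The inequality also changes, from strictly below to at or below. No statement in the protocol reconciles the two.

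A site that followed the cited appendix could admit, or turn away, a subject with reduced clearance contrary to Inclusion 11. This is a safety criterion in a first-in-human study of the intratumoral route, so sites should apply it uniformly. The stake goes no further than that: DLT evaluation, the dose-assignment rule, the sample size and the analyses do not depend on it.

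**Working it through.** **Inputs from the protocol**

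- Inclusion 11: creatinine <1.5×ULN, or clearance ≥50 mL/min.
- Appendix 4: creatinine ≤1.8 mg/dL, or clearance ≥50 mL/min.
- Appendix 4 formula: clearance = (140 − age) × weight × 1.23 / creatinine in µmol/L, multiplied by 0.85 for women.

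**Assumptions not in the documents**

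- A creatinine ULN of 1.0 to 1.3 mg/dL (0.9 to 1.4 in the grid check below).
- 1 mg/dL = 88.4 µmol/L.

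**Step 1: where the rules can differ.** Both are either/or rules with the same clearance alternative. Anyone with clearance ≥50 mL/min passes both. Below 50 mL/min, only the creatinine limit decides.

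- If 1.5×ULN ≤ 1.8, Appendix 4 alone accepts creatinine from 1.5×ULN to 1.8 mg/dL, both ends included.
- If 1.5×ULN > 1.8, Inclusion 11 alone accepts creatinine above 1.8 and below 1.5×ULN, both ends excluded.

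A grid check agreed with this. For each ULN from 0.9 to 1.4 mg/dL it covered both sexes, ages 18 to 90, weights 40 to 120 kg and creatinine 0.50 to 3.00 mg/dL. That made 64,158 combinations per ULN, and no disagreement fell outside the region described.

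**Step 2: size and direction of the gap.** The limits meet where 1.5×ULN = 1.8, that is, at ULN = 1.8/1.5 = 1.2 mg/dL.

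| Assumed ULN (mg/dL) | 1.5×ULN (mg/dL) | 1.8 ÷ (1.5×ULN) | Appendix 4 compared with Inclusion 11 |
|---|---|---|---|
| 1.0 | 1.50 | 1.20 | 20% looser |
| 1.1 | 1.65 | 1.09 | 9% looser |
| 1.2 | 1.80 | 1.00 | differs only at exactly 1.8 |
| 1.3 | 1.95 | 0.92 | about 8% stricter |

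**Step 3: one example in each direction.** Take a man of 70 kg.

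- *ULN 1.0, creatinine 1.6 mg/dL (141.4 µmol/L).* At age 70, clearance is 70 × 70 × 1.23 / 141.4 = 6027/141.4 = 42.6 mL/min. He fails Inclusion 11 (1.6 is not below 1.50) and passes Appendix 4. At age 50, clearance is 90 × 70 × 1.23 / 141.4 = 7749/141.4 = 54.8 mL/min, and both rules accept him.
- *ULN 1.3, creatinine 1.9 mg/dL (168.0 µmol/L).* At age 70, clearance is 6027/168.0 = 35.9 mL/min; at age 50 it is 7749/168.0 = 46.1 mL/min. At both ages he passes Inclusion 11 (1.9 is below 1.95) and fails Appendix 4.

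**Step 4: how body weight limits the gap.** The weight at which clearance reaches 50 mL/min, and the rules agree again, is 50 × creatinine / ((140 − age) × 1.23) for a man. With ULN 1.0, over creatinine of 1.5 to 1.8 mg/dL (132.6 to 159.1 µmol/L):

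- age 50: 6630/110.7 = 59.9 kg to 7956/110.7 = 71.9 kg;
- age 70: 6630/86.1 = 77.0 kg to 7956/86.1 = 92.4 kg.

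Dividing by 0.85 gives the weights for women: 70.5 to 84.6 kg at age 50, and 90.6 to 108.7 kg at age 70. The disagreement therefore falls mainly on older and lighter subjects.

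**The case against.** The strongest reply is that the protocol already settles the matter. Sections 9.3, 9.3.1 and 9.4.3 all place eligibility in Section 9.3, and the title of Appendix 4 presents it as a calculation aid. In Section 9.3.1 the citation is attached to the formula; even in the Synopsis it comes straight after the formula, with only the bracket placed differently. On this reading the appendix sentence is a leftover and not a competing rule. This stands as an argument about which text governs. It does not remove the conflict, because the appendix sentence is worded as a requirement on subjects, and the formula needs no creatinine threshold.

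A second reply is that 1.8 mg/dL may be 1.5×ULN worked out for a laboratory with a ULN of 1.2 mg/dL. That is possible, but the documents do not say so. Even then the rules would differ at exactly 1.8 mg/dL, and at any other ULN they would differ over a range. The loose remark about SI units in Inclusion 11 does not supply the link.

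A third reply is that the point comes too late. SAP Section 7 reports that escalation ended early, and SAP Section 3.2.2 says no expansion subjects will be enrolled. This stands, and it holds the point to a minor correction.

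**Conclusion.** The inconsistency is real, and it is minor. The two creatinine limits differ at any ULN other than 1.2 mg/dL, and at 1.2 they still differ at the boundary value. The disagreement is confined to subjects with clearance below 50 mL/min and creatinine between the limits. Inclusion 11 is the better-supported rule whichever limit is the looser, so Appendix 4 is the text to change.

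The percentages and examples rest on assumed ULNs and the standard unit conversion. That the two limits differ, and where they can disagree, does not. How many subjects were affected cannot be worked out from the documents, and it may be none.

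**What to change.** Delete the eligibility sentence from Appendix 4 and leave only the Cockcroft-Gault formula, so that Inclusion 11 is the single rule. Alternatively, replace the fixed 1.8 mg/dL limit in that sentence with <1.5×ULN.

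The cost is one appendix sentence, with no change to any analysis. The edit would not show which limit sites actually used; only the screening records could. SAP Section 7 drops the protocol-deviation analysis from the abbreviated report, so that analysis would not show it either.
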